# IRB#: 06-044 A(11)

## 9.4 Treatment modifications (all patients)

*For grade 1* perifosine related adverse events, treatment with perifosine will not be interrupted.

For grade 2 perifosine related adverse events

For nausea, vomiting and diarrhea, maintain dosing with symptomatic treatment. The dose of perifosine may be repeated if emesis occurs within 30 minutes of taking the tablet(s) OR all the tablets are seen in the emesis.

For persistent nausea, vomiting or diarrhea, or other persistent grade 2 adverse events despite symptomatic treatment, the daily dose will be reduced by 50 mg.

For grade 3 or 4 perifosine related adverse events

Hold perifosine and re-evaluate the patient at least weekly until toxicity improves to < grade 2 (grade 0 or 1).

If the toxicity resolves in 7 days or less, maintenance (daily) perifosine should be restarted but the daily dose will be reduced by 50 mg.

If the toxicity resolves in 8-14 days, the patient will take another loading dose before reinitiating daily maintenance but the load will by reduced by 200 mg to 400 mg and the maintenance will be reduced to 50 mg. The loading dose will be divided into 4 equal doses of 100 mg each. The first 3 doses should be given with food in the adult day hospital to allow intravenous antiemetic prophylaxis, and 4th dose at bedtime at home. The interval between doses of perifosine should be no less than 4 hours.

If toxicity does not resolve within 14 days, the patient will be withdrawn from the study.

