# IRB#: 06-044 A(11)

surgery. The last dose will be given the night before surgery. Patients on the surgical arm will also undergo a pre-operative FDG-PET following at least 5 days of perifosine and before surgery to correlate metabolic and tissue effects during treatment.

Day of Surgery: Prior to the surgical procedure, tissue freezer vials should be labeled with the patient's protocol study identifier number(s). Additionally, a thermos with liquid nitrogen (preferably), or if not possible, an ice bucket with dry ice should be prepared. All attempts will be made to obtain specimens immediately adjacent to the areas of resection taken for "permanent sections" in order to optimize the likelihood that the tumor seen on permanent sections is representative of that taken for analysis. Once the pathologist has made a diagnosis of "tumor" on frozen section at the time of surgical resection, the tumor tissue should be divided into 50 - 100mg pieces.

At the time of surgery 10ml of blood will be collected for pharmacodynamic analysis.

Following surgery: A post-operative MRI/CT scan should be done no later than 96 hours from surgery. Once patients have recovered from the effects of surgery and demonstrated wound healing, they will restart perifosine (load and maintenance). Patients are not required to have residual disease to continue perifosine. Treatment with perifosine post-operatively should start a minimum of 7 days after surgery. If more than 14 days have passed since the post-operative MRI was performed, new baseline brain MRI (with MR Perfusion if possible) and brain FDG-PET sans must be performed.

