### IRB#: 06-044 A(11)

#### .0 **BIOSTATISTICS**

The historical values for comparison are from a database of 225 GBM patients enrolled in 8 previous phase II studies (in which none of the treatments were considered particularly effective.[24] In this database, the 6 month PFS was 15% for GBM. The 6 month PFS for patients treated with BCNU for recurrence/progression was 17.5%.[3] Therefore, we would expect 6 month PFS to be less than 20%.

We will utilize a Simon two-stage design in which the primary endpoint is the progression rate at 6 months. All patients will be followed for 6 months and progression or death due to disease will be considered an event. Assuming a 6 month progression free survival rate of 20% is considered promising, a 6 month progression free survival rate of 5% is considered not promising, and the probabilities of a type I error (falsely accepting a non-promising therapy) and type II error (falsely rejecting a promising therapy) are set at 0.10 and 0.10, respectively. In the first stage of this design, 12 patients with GBM will be accrued. If at least 1 patient with GBM does not progress at the 6 month time among these 12 patients, then an additional 25 patients with GBM (for a total of 37) will be accrued to the second stage, otherwise the trial will be terminated. Note that enrollment of patients with both GBM and non-GBM malignant gliomas will continue while the first 12 patients with GBM are followed for PFS. However, if 0 of these first 12 reach 6mPFS, then enrollment will terminate; in that event, any patients still on trial with any histology may continue until progression or death at the discretion of the treating physician. At the end of the trial, if 3 or less patients with GBM are progression free at 6 months, the study will be declared negative. This design yields at least a 0.90 probability of a positive result if the true response rate is at least 20% and yields a 0.90 probability of a negative result if the true response rate is 5%.

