Up to 20 patients with anaplastic glioma and evaluable disease at study entry (i.e., did not undergo gross total resection as the most recent therapy prior to registration) will be accrued. Endpoints such as response, one-year survival probability, overall survival and progression-free survival will be computed in order to gain preliminary data for these other malignant glioma subtypes. However, the historical controls for patients with anaplastic glioma are less well defined than for GBM; therefore, only patients with GBM will be included in analyses of efficacy and the two-stage design will be applied only to the GBM cohort.

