## IRB#: 06-044 A(11)

the drug is considered promising (defined above) after either the first stage enrolling 12 patients with GBM or complete accrual of the total cohort of 37 patients with GBM. Any additional patients enrolled through this mechanism will be included in the primary analysis of efficacy (6mPFS) and the total cohort will be increased from 37 patients with GBM to a maximum of 47 patients with GBM (37 + 10 additional surgical patients in the unlikely circumstance that none of the initial 37 patients are enrolled on the surgical arm). Therefore, the maximum enrollment is up to 57 patients (37 with GBM, not on surgical substudy; up to 10 additional patients with anaplastic glioma; up to 10 additional patients on surgical stubstudy if not already accrued).

Although patients on the surgical substudy will have resections of tumor at the initiation of treatment, the natural history of recurrent GBM strongly supports the concept that nearly all patients will have tumor progression by 6 months if no further treatment or ineffective treatment is provided post-operatively. For example, a review of patients with recurrent GBM treated for first relapse at the MD Anderson Cancer Center also supports the concept that gross total resection does not impact on 6-month PFS rate. During the time from of 2001-2003, 220 patients were treated at MD Anderson for first relapse or progression of GBM. There was no difference in 6-month PFS between those patients who had a gross total resection at relapse compared with all other patients. Hence, we plan to combine data from patients on and not on the surgical substudy in efficacy analyses.

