## IRB#: 06-044 A(11)

There are several different mechanisms by which clinical trials are monitored for data, safety and quality. There are institutional processes in place for quality assurance (e.g., protocol monitoring, compliance and data verification audits, therapeutic response, and staff education on clinical research QA) and departmental procedures for quality control, plus there are two institutional committees that are responsible for monitoring the activities of our clinical trials programs. The committees: *Data and Safety Monitoring Committee (DSMC)* for Phase I and II clinical trials, and the *Data and Safety Monitoring Board (DSMB)* for Phase III clinical trials, report to the Center's Research Council and Institutional Review Board.

During the protocol development and review process, each protocol will be assessed for its level of risk and degree of monitoring required. Every type of protocol (e.g., NIH sponsored, in-house sponsored, industrial sponsored, NCI cooperative group, etc.) will be addressed and the monitoring procedures will be established at the time of protocol activation.

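### The only trial-level stopping rule and the gate on the surgical extension use efficacy alone, with no cumulative toxicity trigger stated; separately, the enrolment maximum of 57 does not add up

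*Combined protocol and SAP*

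**What the plan says.** **Trial-level rule.** Section 14.0 accrues 12 GBM patients in stage 1 and stops for futility: "However, if 0 of these first 12 reach 6mPFS, then enrollment will terminate". Accrual does not wait for that result: "Note that enrollment of patients with both GBM and non-GBM malignant gliomas will continue while the first 12 patients with GBM are followed for PFS".

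**Gate on the surgical extension.** If fewer than 10 patients have entered the surgical substudy at full enrolment, the trial stays open only if "the drug is considered promising (defined above) after either the first stage enrolling 12 patients with GBM", or after the full 37. The definition referred to is the 6mPFS criterion.

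**Patient-level toxicity rules.** Section 9.4 sets holds and dose reductions, and ends: "If toxicity does not resolve within 14 days, the patient will be withdrawn from the study". Section 13.1 lists reasons to stop an individual's treatment. Section 9.5 makes post-operative restart conditional on recovery, wound healing and at least 7 days.

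**Oversight and reporting.** Section 16.2 says "there are two institutional committees that are responsible for monitoring the activities of our clinical trials programs", one of them a DSMC for phase I and II trials, and leaves monitoring procedures to be fixed at activation. Section 17.2 sends serious adverse events (SAEs) to the IRB within 5 calendar days and to the company within 24 hours. Section 17.2.2 puts adverse events on the case report form, related or not.

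**Enrolment.** Section 14.0 first allows "Up to 20 patients with anaplastic glioma and evaluable disease at study entry". Under the surgical arm it then states: "Therefore, the maximum enrollment is up to 57 patients", made up of 37 GBM, up to 10 anaplastic and up to 10 extra surgical patients.

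**The concern.** A run of related severe toxicity could be handled one patient at a time, by dose cuts and withdrawals, without anything in this document calling for a look at the rate. The SAE route need not fill that gap. Under Section 17.2.3 a grade 3 event is an SAE only if it meets another criterion, such as hospitalisation, and grade 4 nausea and emesis are carved out of the life-threatening criterion. Yet the grade 3 events described for this dose in phase I were fatigue and nausea.

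The population adds some weight. Eligibility extends down to KPS 50 with no limit on prior therapies. Surgical patients take drug until the night before resection and repeat the loading dose afterwards. The continuous-schedule phase I trial included one glioblastoma patient.

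The enrolment figure matters because the stated maximum is the number of patients who may be exposed.

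**Working it through.** **1. The plan's own figures.** Simon design, stop at 0/12, positive at 4 or more of 37. P(positive) is the sum over x = 1 to 12 of P(X1 = x) times P(X2 >= 4 - x), with X1 ~ Bin(12, p) and X2 ~ Bin(25, p).
- p = 0.20: 0.902 (stated: at least 0.90).
- p = 0.05: 0.093, so P(negative) = 0.907 (stated 0.90).

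The design reproduces and is not in dispute.

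**2. What the existing gate says about toxicity.** P(pass stage 1) = 1 - (1 - p)^12, where p is the 6mPFS rate.
- p = 0.05: 1 - 0.540 = 0.460.
- p = 0.20: 1 - 0.069 = 0.931.

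The toxicity rate enters neither figure. The readout may take up to six months after the 12th GBM patient starts. No accrual rate is given; at an assumed 1, 2 or 4 patients a month, that wait adds 6, 12 or 24 patients (6 months x rate).

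**3. Toxicity data at this dose.** Section 3.5.2 reports, among 12 patients, 3 with grade 3 fatigue and 1 with grade 3 nausea, and no further grade 3 events recorded as probably drug-related. The text calls this dose level 2, but Table 6 shows 12 patients only at 600/100 mg, so I take it as this trial's dose. Overlap is not stated, so 3 or 4 patients were affected:
- 3/12 = 25% (exact 95% limits 5.5% to 57.2%).
- 4/12 = 33% (9.9% to 65.1%).

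The head and neck phase II trial (19 patients, same regimen) describes two grade 3 events in wording that is not exhaustive, so it gives no rate. Table 7 (continuous regimen, n = 57) covers gastrointestinal events only and omits fatigue.

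**4. An example review boundary.** Count treated patients with probably related grade 3-5 toxicity and prompt review at >=5/10, >=8/20, >=11/30, >=14/40 or >=17/50. Exact sequential binomial probability of crossing at any look:

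| True rate | P(cross) |
|---|---|
| 10% | 0.002 |
| 20% | 0.07 |
| 25% | 0.22 |
| 30% | 0.46 |
| 33% | 0.64 |
| 40% | 0.90 |
| 50% | >0.99 |

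The first look comes 28 days after the 10th treated patient starts.

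**5. Enrolment arithmetic.**
- As stated: 37 + 10 + 10 = 57.
- With the 20 anaplastic patients allowed earlier in the same section: 37 + 20 + 10 = 67.
- Cross-check: the surgical-arm text raises the GBM cohort to at most 47, and 47 + 20 = 67.

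**The case against.** The strongest reply is that the missing piece may simply sit elsewhere. Section 16.2 refers to institutional plans approved by the NCI, says each protocol is assessed for risk, and defers procedures to activation. A reader might infer from the silence here that the trial has no safety oversight. The documents do not support that, and this part of the objection stands in full.

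Other data streams also exist. Adverse events go on the case report form, gastrointestinal severity is scored in a weekly diary (Section 10.1), grade 4 diarrhoea remains an SAE, and the last SAE criterion is broad. The dose is below the phase I maximum tolerated dose (600/100 against 900/100 mg). What remains is that nothing here says these data reach the DSMC as a rate.

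A reader might also want the boundary to pause enrolment automatically. The documents give no acceptable toxicity rate, and at the phase I rate of 25%-33% the example is crossed 22%-64% of the time. Adding a pause for any probably related death would give about a 30% or 48% chance of at least one pause at a 20% toxicity rate and assumed death rates of 0.5% or 1%, treated as independent. An automatic pause is a trade-off that the text does not settle.

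Finally, attribution is imprecise. Section 17.2.1 reserves the probable category for events where other causes are unlikely, so fatigue in recurrent GBM could well be graded as possible and escape a count limited to probable events.

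On enrolment, 57 could be rescued by supposing that the 10 extra surgical patients are anaplastic. The same paragraph adds them to the GBM cohort, so that reading fails.

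**Conclusion.** Two conclusions, of different kinds.

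**Toxicity count: a cheap improvement, not an error.** As written, the trial-level stop and the surgical gate depend only on 6mPFS, and no cumulative toxicity count or look time is given. Confidence is high only that this document states no trigger; the activation procedures may contain one. The Simon design and the 6mPFS test are sound and unaffected. The example boundary separates a 20% rate (crossed 7% of the time) from 40% (90%). It rests on independent patients and on an acceptable rate that I have assumed, so it illustrates the cost of a rule and does not prescribe the numbers.

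**Enrolment maximum: wrong as written.** The two statements differ by 10 patients, 57 against 67. This is a separate matter and adds no weight to the toxicity point.

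Overall the point lies between something to consider and something that should be done.

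**What to change.** **1. Toxicity report, in Sections 14.0 and 16.2.**
- Send the DSMC a cumulative count, over all treated patients, of those with grade 3-5 toxicity (CTCAE v3.0) possibly or probably related to perifosine, with the two categories shown separately.
- Report each time 10 more patients reach 28 days from first dose or stop early. For surgical patients, count from the first pre-operative dose.
- A pre-set number with probably related events, for example the boundary above, prompts DSMC review. The DSMC decides whether to pause. The investigators and DSMC set the final numbers.
- Any possibly or probably related death gets expedited DSMC review without an automatic pause.
- Include serious post-operative complications in the same report, without a separate boundary.
- If the activation monitoring plan already holds an equivalent trigger, cite it instead.

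**2. Enrolment.** Correct either the 20 anaplastic patients or the total of 57. If 20 is meant, the maximum is 67.

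**Cost.** Some protocol wording and a short periodic report, largely from data already recorded; post-operative complications need a working definition. No new committee, visits or patients. The downside is that some reviews will be triggered when toxicity is acceptable: 7% of trials at a true rate of 20%, and more if rates near those of phase I are judged tolerable.

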#### Surgical arm

In order to obtain specimens for study of the tissue pharmacokinetics of perifosine in tumors, as well as the molecular effects of perifosine in tumor tissue, we plan to accrue subjects to a preoperative treatment arm. There is no upper bound on the number of patients that can be entered into this substudy. However, if the study reaches the total enrollment and fewer than 10 patients have entered this substudy, the trial will be kept open to accrue at least 10 surgical arm patients. Note, the study will only be kept open if

## IRB#: 06-044 A(11)

the drug is considered promising (defined above) after either the first stage enrolling 12 patients with GBM or complete accrual of the total cohort of 37 patients with GBM. Any additional patients enrolled through this mechanism will be included in the primary analysis of efficacy (6mPFS) and the total cohort will be increased from 37 patients with GBM to a maximum of 47 patients with GBM (37 + 10 additional surgical patients in the unlikely circumstance that none of the initial 37 patients are enrolled on the surgical arm). Therefore, the maximum enrollment is up to 57 patients (37 with GBM, not on surgical substudy; up to 10 additional patients with anaplastic glioma; up to 10 additional patients on surgical stubstudy if not already accrued).

Although patients on the surgical substudy will have resections of tumor at the initiation of treatment, the natural history of recurrent GBM strongly supports the concept that nearly all patients will have tumor progression by 6 months if no further treatment or ineffective treatment is provided post-operatively. For example, a review of patients with recurrent GBM treated for first relapse at the MD Anderson Cancer Center also supports the concept that gross total resection does not impact on 6-month PFS rate. During the time from of 2001-2003, 220 patients were treated at MD Anderson for first relapse or progression of GBM. There was no difference in 6-month PFS between those patients who had a gross total resection at relapse compared with all other patients. Hence, we plan to combine data from patients on and not on the surgical substudy in efficacy analyses.

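### Surgical top-up patients join the primary analysis with no cut-off set for 38 to 47 GBM patients; if passing stage 1 opens the extension and 3 or fewer is kept, type I error passes 0.10 at the second added patient (0.1055; at most 0.156)

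*Combined protocol and SAP*

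**What the plan says.** Section 14.0 (Biostatistics) describes a Simon two-stage design for GBM. A 6-month progression-free rate of 5% is not promising and 20% is promising, with both error probabilities set at 0.10. Stage 1 has 12 patients and continues if at least 1 is progression free. Stage 2 adds 25, for a total of 37. The final rule is that "if 3 or less patients with GBM are progression free at 6 months, the study will be declared negative". The section claims a probability of at least 0.90 of a positive result at 20% and of 0.90 of a negative result at 5%.

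The Surgical arm subsection adds an extension, meant to bring in at least 10 surgical patients: "if the study reaches the total enrollment and fewer than 10 patients have entered this substudy, the trial will be kept open". The condition is that "the drug is considered promising (defined above) after either the first stage enrolling 12 patients with GBM or complete accrual"; the accrual meant here covers all 37 GBM patients. Those who enter this way are not kept apart from the efficacy result: "Any additional patients enrolled through this mechanism will be included in the primary analysis of efficacy (6mPFS"). The same sentence then sets the ceiling on GBM numbers: "the total cohort will be increased from 37 patients with GBM to a maximum of 47 patients with GBM". The full ten would be needed only "in the unlikely circumstance that none of the initial 37 patients are enrolled on the surgical arm". Histology is restricted elsewhere in Section 14.0: "only patients with GBM will be included in analyses of efficacy".

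**The concern.** The final rule and its error rates were worked out for 37 patients. Adding patients while holding the required number of successes at 4 makes a positive result easier to reach by chance. The added patients would be enrolled to complete a tissue quota, not to answer the efficacy question, yet they could turn 3 successes in 37 from a negative trial into a positive one. This is the trial's primary aim and its only go/no-go rule. With nothing stated for 38 to 47, the analyst would have to choose the cut-off after the sample size, and possibly the outcomes, are known.

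Whether the error rate actually rises depends on what opens the extension, and the condition can be read in two ways:

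- **Stage 1 is enough.** The text says either after the first 12 or after the full 37. Every trial that reaches 37 has already had at least 1 success in 12, so all of them qualify. The trigger, reaching total enrolment, fits this reading: at that moment the last patients' 6-month outcomes are not yet known.
- **The 37-patient result must be positive.** At least 4 of 37 must be progression free first. The cut-off is then already met and the added patients cannot change the decision.

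**Working it through.** **Inputs** (all from Section 14.0): null rate 0.05; alternative 0.20; error limits 0.10 and 0.10; stage 1 size 12, continue if at least 1 success; total N = 37, rising to at most 47; positive if at least 4 successes.

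**Formula.** With X1 ~ Bin(12, p) and X2 ~ Bin(N − 12, p):

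P(positive) = Σ over x1 = 1 to 12 of P(X1 = x1) × P(X2 ≥ max(0, 4 − x1)).

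**Step 1: the plan's own figures.** At N = 37 this gives a type I error of 0.0935 and power of 0.9024. The probability of stopping at stage 1 when p = 0.05 is 0.95^12 = 0.540. The stated properties hold for 37.

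**Step 2: more GBM patients, stage 1 enough to open the extension.** The middle columns keep the cut-off of 3 or fewer for a negative result. The right-hand columns require at least 5 successes.

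| N | Type I error, need 4 | Power, need 4 | Type I error, need 5 | Power, need 5 |
|---|---|---|---|---|
| 37 | 0.0935 | 0.9024 | 0.0321 | 0.8482 |
| 38 | 0.0994 | 0.9068 | 0.0351 | 0.8591 |
| 39 | 0.1055 | 0.9106 | 0.0383 | 0.8686 |
| 40 | 0.1116 | 0.9138 | 0.0417 | 0.8770 |
| 42 | 0.1241 | 0.9189 | 0.0488 | 0.8908 |
| 43 | 0.1303 | 0.9209 | 0.0526 | 0.8964 |
| 44 | 0.1366 | 0.9225 | 0.0565 | 0.9013 |
| 47 | 0.1556 | 0.9261 | 0.0688 | 0.9124 |

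With the cut-off kept, the 0.10 limit is passed at N = 39, the second added patient. At N = 47 the probability of a negative result at a true 5% is 1 − 0.1556 = 0.844, against the stated 0.90. For N = 39 to 43 neither cut-off meets both limits. Requiring 5 meets both only for N = 44 to 47.

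**Step 3: how often the decision turns.** At p = 0.05, the probability of passing stage 1 and having 1 to 3 successes in 37 is 0.3662. The probability of doing so and then reaching 4 or more after m added patients is 0.0120 for m = 2, 0.0306 for m = 5 and 0.0621 for m = 10. As shares of the 0.3662, these are 3.3%, 8.4% and 17.0%. Check: 0.0935 + 0.0621 = 0.1556.

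**Step 4: extension only after at least 4 of 37.** With the cut-off kept, P(positive) stays at 0.0935 (p = 0.05) and 0.9024 (p = 0.20) for every N.

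**Step 5: how many might be added.** The documents give no share of patients entering the surgical arm, so the shares here are assumptions. The GBM-only column takes S ~ Bin(37, f) and adds max(0, 10 − S) GBM patients. The other columns let anaplastic patients also fill the quota of 10, with each added patient GBM with probability 37/57 or 37/47. Two versions are needed because Section 14.0 allows up to 20 anaplastic patients in one place and counts 10 in its enrolment total.

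| Assumed surgical share | Mean type I error, GBM only | With 10 anaplastic | With 20 anaplastic |
|---|---|---|---|
| 10% | 0.132 | 0.119 | 0.111 |
| 20% | 0.110 | 0.100 | 0.096 |
| 30% | 0.097 | 0.094 | 0.0935 |

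**The case against.** The strongest objection is that the inflation needs the extension to open on stage 1 alone. Section 14.0 uses the word promising for a 20% rate and never for 1 success in 12, which is 8.3%. If stage 1 were enough, mentioning the full 37 would add nothing, so a reader could fairly take the 37-patient result as the test for going beyond 37. On that reading the error stays at 0.0935. This stands as a reason to call the condition ambiguous. It does not remove the other reading, because the either/or wording permits it and promising is not defined as a count of successes.

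Second, the final rule speaks of the end of the trial and is not tied to 37, so it can be read as carrying 3 or fewer forward. That is fair, but it is exactly the case that breaks the stated error rate.

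Third, the size is modest. The 0.156 needs no surgical patients among the first 37. At assumed surgical shares of 20% to 30% the mean error is close to or below 0.10. This stands as a limit on severity. Two added GBM patients are still enough to pass 0.10, and if only GBM patients fill the quota, that happens whenever 8 or fewer of the 37 enter the surgical arm.

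Fourth, including surgical patients was a deliberate choice, supported by the argument that resection does not affect 6-month progression-free survival. That argument supports pooling but does not address the cut-off when the sample grows.

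**Conclusion.** The concern holds. The stated 0.90 probability of a negative result at a true 5% is established only for 37 GBM patients, while the plan lets the primary analysis grow to 47 with no rule for the larger sizes. If passing stage 1 opens the extension and the cut-off stays at 3, type I error is 0.1055 with two added GBM patients and at most 0.156 with ten. If at least 4 of 37 is required first, it stays at 0.0935. The plan does not say which applies. The figures assume independent patients with a common rate of exactly 5%, and that N counts GBM patients only. Added anaplastic patients would make the GBM excess smaller. Power is not at issue, being 0.902 already at 37. The point should be fixed: the inflation is conditional and usually small, but it affects the sole decision rule.

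**What to change.** In Section 14.0, state that the primary decision uses the first 37 GBM patients enrolled with the existing cut-off, and that surgical patients enrolled after the 37th contribute to tissue, pharmacokinetic and supportive efficacy analyses only. This holds type I error at 0.0935 and power at 0.902 on either reading. Also state which result opens the extension: at least 1 of 12, or at least 4 of 37.

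If the added patients are to stay in the primary analysis, requiring at least 4 of 37 before the extension and keeping the cut-off also holds the error at 0.0935, but the added patients then cannot affect the decision. Scaling the cut-off with the final number is weaker, since neither cut-off meets both limits at 39 to 43 patients.

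The cost is one or two sentences, with no extra patients and no lost tissue data. The anaplastic figure (20 in one place, 10 in the enrolment total) should be reconciled in the same edit.
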